In cases where the research is of therapeutic intent or is designed to investigate areas that would necessarily require certain populations who may not speak English, the researcher is required to make efforts to recruit and include non-English speaking individuals. However, there are studies in which it would be reasonable to limit subjects to those who speak English. Some examples include pilot studies, small unfunded studies with validated instruments not available in other languages, studies with numerous questionnaires, and some non-therapeutic studies which offer no direct benefit.

Response:

We will not enroll non-English speaking individuals. Enrollment in this study is not large (20 participants in total) and there is no reason to believe that the study would be withholding benefit from non-English speaking subjects.

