Subjects will come back within 2 weeks and will arrive after having fasted overnight (10 hours) at 7 to 7:30 am. They will then be randomized to either active tDCS or sham tDCS with block randomization (block size of 10). We will test urine pregnancy test to rule out pregnancy. Pregnant subject will be excluded from the study. We will also administer the three-factor eating questionnaire (Stunkard and Messick, 1985), which measures eating habits and attitudes toward food, weight and dieting, and a personality questionnaire, the Big Five (Costa and McCrae, 1989). We will evaluate cognitive responses to food with a 20-minute computerized task designed to engage the inhibitory control circuit when confronted with food stimuli, as well as engaging the other two components of executive function: working memory and cognitive flexibility. The task consists of 3 parts: a version of a Go/No-Go (GNG) task modified for food; an N-back memory task with food images, similar to a task used in a previous study; and a combined N-back and GNG task. In the food modified GNG task subjects have to press the space bar of a computer in response to pictures of low-calorie food, refraining from pressing when the pictures are of high-calorie food (25% of the time). In the N-back task, subjects will press the space bar when the picture displayed matches the picture displayed two images before. In the combined task, the subject will press the space bar when a picture of low-calorie food matches the picture displayed two images before, while refraining from pressing when a high-calorie food matches the picture displayed two images before.

Blood sample for BDNF and COMT gene test will be collected. We will also collect blood sample for plasma insulin and glucose level. We will download data from the continuous glucose monitor.

Subjects assigned to active tDCS group will receive 30 min of anodal tDCS delivered with a neuroConnVR DCSTIMULATOR device (neuroConn GmbH, Ilmenau, Germany), at a constant current of 2 mA (with a 30-second ramp at on- and offset) using two sponge electrodes soaked in a sterile 0.9% sodium chloride solution. The anode electrode will be placed over F3 (10–20 EEG system), with the cathode electrode placed over the contralateral supraorbital area, above the right eyebrow. This montage was used in a recent study that showed reduction of body weight and intake of soda and fat in a sample of obese subjects.

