19.0 Provisions to Monitor the Data to Ensure the Safety of Subjects

- N/A:** This study is not enrolling subjects, or is limited to records review procedures only. This section does not apply.

NOTE: Minimal risk studies may be required to monitor subject safety if the research procedures include procedures that present unique risks to subjects that require monitoring. Some examples include: exercising to exertion, or instruments that elicit suicidality or substance abuse behavior. In such cases, N/A is not an acceptable response.

19.1 Describe the plan to periodically evaluate the data collected regarding both harms and benefits to determine whether subjects remain safe.

Response:

According to previous studies, active tDCS was associated with a higher prevalence of skin redness compared with control group. Other possible adverse reaction reported in the past include scalp burning, tingling, sleepiness, difficulty with concentrating, headache, neck pain and scalp pain, but the prevalence of these reactions was not found to be different from control group. These side effects are generally transient and resolve with time without active intervention. Contraindications for the use of tDCS include underlying psychiatric illness, personal or family history of seizures, underlying skin disorders, history of implanted pacemaker, medication pump, vagal stimulator, deep brain stimulator, TENS unit, ventriculoperitoneal shunt or any metallic implant on the head. Although not a direct contraindication, scarring within the brain may modify the effects of the tDCS and therefore prior neurosurgical procedures or radiation treatment to the brain are also considered contraindications. Subjects with any of these known medical conditions will be excluded. Immediately before and after tDCS administration, we will systematically monitor the presence of adverse events using a standard tDCS safety questionnaire that has been previously published (Brunoni et al., 2011). Subjects who report significant side effects related to the tDCS may also be excluded based on the investigator's judgement.

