19.8 Describe the statistical tests for analyzing the safety data to determine whether harm is occurring.

Response: We will calculate the percentage of participants that developed any adverse reaction during the course of the study. We will use Fisher exact test to compare the percentage of participants that developed serious adverse reaction (which leads to withdrawal of subject) between group with active tDCS and sham tDCS. We will use two sample exact test for incidence rate data to compare the incidence of mild adverse reaction (which did not lead to withdrawal of subjects) between the two groups.

19.9 Describe any conditions that trigger an immediate suspension of the research.

Response: Inability to tolerate the tDCS administration, continuous glucose monitor or blood draw

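### The exact rate test for mild reactions in 19.8 has no defined event unit or denominator and, if every reaction is counted, ignores clustering within the 20 subjects

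*Combined protocol and SAP*

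**What the plan says.** Section 19.8 answers the template question "Describe the statistical tests for analyzing the safety data to determine whether harm is occurring" with three elements:

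- **Any reaction.** "We will calculate the percentage of participants that developed any adverse reaction during the course of the study". No between-arm test is named.
- **Serious reactions**, meaning those that lead to withdrawal. "We will use Fisher exact test to compare the percentage of participants that developed serious adverse reaction".
- **Mild reactions.** "We will use two sample exact test for incidence rate data to compare the incidence of mild adverse reaction", where mild means a reaction "which did not lead to withdrawal of subjects) between the two groups".

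The first two count participants. The third moves to rates, but gives no event unit, no denominator and no significance level.

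On data collection, section 19.1 states: "Immediately before and after tDCS administration, we will systematically monitor the presence of adverse events using a standard tDCS safety questionnaire". Section 21.2 adds the last visit, and sections 19.4 and 19.5 add reports by telephone. Section 10.1 sets five stimulation sessions (visits 1 to 5) and a sixth visit four weeks later. Section 21.1 lists skin redness and seven other possible symptoms of stimulation. It also says that every sham patient in the earlier nine-patient study had difficulty concentrating.

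**The concern.** A two-sample exact test for incidence rates takes the event total in each arm as a Poisson count, so events must be independent of each other. In this trial the independent units are the subjects. A mild reaction by definition leaves the subject in the study, and the questionnaire comes back at the next session with the same list of symptoms. Someone with a sensitive scalp or recurrent headaches can therefore supply many events. If these are pooled and tested as independent, the test overstates the information in the data, and a few people can produce an apparent arm difference.

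This is the only between-arm comparison of mild harm in the plan. Section 19.1 expects side effects to be generally transient, so mild reactions are likely to be most of the safety data.

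**Working it through.** The plan states no power, alpha or p-value for its safety tests, so there is no figure to reproduce. The check is how the named test behaves on data of the kind the plan collects.

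**Inputs from the documents**
- Total sample: 20 ("Enrollment in this study is not large (20 participants in total", section 6.4).
- Allocation: "randomized to either active tDCS or sham tDCS with block randomization (block size of 10" (section 10.1). The ratio is not stated; 10 per arm is assumed.
- Five sessions per subject, plus a last visit.

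**Assumed, because the documents are silent**
- Two-sided 5% level, equal exposure in the two arms, every reaction counted.
- Mean events per subject m = 1, 2 or 5.
- Between-subject coefficient of variation (CV) of the reaction rate: 0, or 0.5 to 1.0.

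**The test.** With equal exposure, the exact rate test conditions on the total number of events n. Under no difference, the active-arm count is Binomial(n, 0.5).

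**A worked case.** Two subjects in one arm react at all five sessions and nobody else reacts.
- Events: 2 × 5 = 10 against 0. Exact rate test: p = 2 × 0.5^10 = 0.002.
- Subjects: 2/10 against 0/10. The chance that both reactors fall in one given arm is C(10,2)/C(20,2) = 45/190 = 0.237. Two-sided Fisher p = 2 × 0.237 = 0.47.
- A permutation test of the per-subject counts also gives 0.47.

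**False-positive rate with no true difference** (simulation, 20,000 trials per scenario). Rates vary between subjects by a gamma distribution, so the variance-to-mean ratio (VMR) of the counts is 1 + m × CV². For example, m = 2 and CV = 1 give 1 + 2 × 1 = 3.

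| Mean events per subject | CV 0 (independent) | CV 0.5 to 1.0 | VMR at CV 0.5 to 1.0 |
|---|---|---|---|
| 1 | 3% | 5% to 12% | 1.25 to 2 |
| 2 | 3-4% | 8% to 22% | 1.5 to 3 |
| 5 | 4% | 17% to 39% | 2.25 to 6 |

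**One symptom scored yes or no at five sessions** (per-session risk 0.1 to 0.5), by within-subject correlation:

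| Correlation | False positives |
|---|---|
| 0 (equal risk in everyone) | 0.4% to 1.6% |
| 0.2 | 3.0% to 7.1% |
| 0.5 | 9% to 17% |
| 0.8 | 16% to 26% |

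**Subject-level tests.** These were run over the same symptom scenarios and over counts with means 1, 2 and 5 and VMR 1 to 5. The permutation test of per-subject counts rejected in about 0.5% to 4.5% of trials. Fisher's test on subjects with at least one reaction rejected in 0% to 1.4%. Both stay below 5%.

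**The case against.** The strongest reply is that 19.8 never says repeat reactions are counted. If only a subject's first mild reaction enters, with time at risk ending there, the independence objection disappears. That is right, and it is why the point is conditional. But the move from percentages of participants to a rate makes counting all events the more natural reading, and no first-event rule appears anywhere. On either reading the unit and denominator must be written down.

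A second reply is that the size of the error is assumed. That also stands. A reader might infer that the p-value is simply wrong. The documents do not support that: with little variation between subjects the test holds its level or is conservative, and inflation starts at a VMR of roughly 1.3 to 1.5.

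A reader might also infer that symptoms already present before a session are counted as reactions to it. Section 19.8 does not say so. It speaks of reactions that developed, and asking before and after stimulation could supply a baseline for each session.

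Third, the consequence is limited. This is a 20-subject pilot, no stopping rule uses the test (19.9 ties suspension to intolerance), and the percentage of participants with any reaction will be reported anyway. All of this is true and limits the weight of the point. It does not justify keeping a p-value that two people can drive.

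**Conclusion.** The point holds in conditional form. Section 19.8 leaves the event unit and denominator undefined. If all reactions are counted, the named test ignores within-subject clustering and can reject far too often.

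For total counts that vary between subjects, the error runs from close to nominal at a mean of 1 event per subject and CV 0.5 to 39% at mean 5 and CV 1.0. For a single symptom with equal risk in everyone it is about 1%, so the error can go either way. These figures rest on 10 per arm, a two-sided 5% level, equal exposure, and assumed event rates and variation. The worked case (0.002 against 0.47) needs no assumed rate or variation, only that every reaction is counted.

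The effect is on how mild harm is reported and carried forward from the pilot. No stopping decision depends on it.

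**What to change.** In 19.8, replace the incidence-rate test with a comparison that has the subject as its unit:

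1. State what counts as one mild reaction, including how the pre-session answer is used.
2. Compare the arms on the number of subjects with at least one mild reaction, by Fisher's exact test.
3. Support this with an exact permutation (Wilcoxon) test of each subject's total mild reactions divided by visits attended. Include reactions reported at the last visit and by telephone. The division allows for subjects who leave early.
4. Report individual symptoms by arm descriptively, without a test for each, so that eight or more symptoms do not bring in multiple testing.

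The third item is needed because Fisher's test says little when nearly everyone reacts. At a mean of 5 independent events, the chance of none is e^-5 = 0.7%, or 20 × 0.007 = 0.1 subjects expected without a reaction.

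The cost is a short edit to 19.8, using reports that the plan already collects. The drawback is somewhat less power if events really were independent.

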20.0 Withdrawal of Subjects

N/A: This study is not enrolling subjects. This section does not apply.

20.1 *Describe anticipated circumstances under which subjects may be withdrawn from the research without their consent.*

Response: Inability to tolerate the tDCS administration, continuous glucose monitor or blood draw. The principal investigator of the study can remove a participant from the research study without their approval if for any reason he/she feels is appropriate, including: severe side effect, injury or medical condition which may place subjects at risk of further complications if he/she continues to participate, failure to keep scheduled appointments, or other administrative reasons.

If any of the subjects become pregnant during the period of study, he/she will need to withdraw from the study.

20.2 *Describe any procedures for orderly termination.*

NOTE: Examples may include return of study drug, exit interview with clinician. Include whether additional follow up is recommended for safety reasons for physical or emotional health.

Response:

We will recommend that the subject come back for an exit visit to make sure he/she is not experiencing side effect from tDCS. However, they can also follow up with us in the clinic since the subjects are recruited from our clinic patients. They will also be asked to return the continuous glucose monitor after the study.

20.3 *Describe procedures that will be followed when subjects withdraw from the research, including retention of already collected data, and partial withdrawal from procedures with continued data collection, as applicable.*

Response: If a subject withdraws from the research, the data collected to that point will be used toward the research finding.

21.0 Risks to Subjects

21.1 *List the reasonably foreseeable risks, discomforts, hazards, or inconveniences to the subjects related to their participation in the research. Consider physical, psychological, social, legal, and economic risks. Include a description of the probability, magnitude, duration, and reversibility of the risks.*

NOTE: Breach of confidentiality is always a risk for identifiable subject data.

Response: Insertion of cannula or drawing blood may result in pain, a feeling of faintness, irritation of the vein, bruising, bleeding, or later infection at the puncture site.

However, risk of infection is very small and treatable. Too much blood collection can potentially lead to hypotension and dizziness. If subjects develop these symptoms, we will stop blood draw.

According to previous studies, active tDCS was associated with a higher prevalence of skin redness compared with control group. Other possible adverse reaction reported in the past include scalp burning, tingling, sleepiness, difficulty with concentrating, headache, neck pain and scalp pain, but the prevalence of these reactions was not found to be different from control group. These side effects are generally transient and resolve with time without active intervention. Difficulty with concentrating is mild and transient. And according to previous study (reference 9), all patients who received sham stimulation also developed difficulty with concentrating, which means this is probably not a side effects of tDCS. However, we list it as a possible effect because the sample size of previous study is small and this symptom was reported by study participants.

Continuous glucose monitor use is occasionally associated with insertion site discomfort or skin irritability. The effect is generally mild and resolve without intervention. Another potential risk is breach of confidentiality. The measures to prevent it are mentioned above.

21.2 Describe procedures performed to lessen the probability or magnitude of risks, including procedures being performed to monitor subjects for safety.

Response: We will collect no more than 50 ml of blood on each visit. We will follow standard sterilization procedure.

Contraindications for the use of tDCS include underlying psychiatric illness, personal or family history of seizures, underlying skin disorders, history of implanted pacemaker, medication pump, vagal stimulator, deep brain stimulator, TENS unit, ventriculoperitoneal shunt or any metallic implant on the head. Although not a direct contraindication, scarring within the brain may modify the effects of the tDCS and therefore prior neurosurgical procedures or radiation treatment to the brain are also considered contraindications. Subjects with any of these known medical conditions will be excluded. Immediately before and after tDCS administration and on the last visit of the study, we will systematically monitor the presence of adverse events using a standard tDCS safety questionnaire that has been previously published (Brunoni et al., 2011). Subjects who report significant side effects related to the tDCS may also be excluded based on the investigator's judgement.

Continuous glucose monitor use is occasionally associated with insertion site discomfort or skin irritability. The effect is generally mild and resolve without intervention. We will demonstrate the correct way of using continuous glucose monitor to subjects to minimize the side effects. We will also ask them if they experience any side effects on the visit after continuous glucose monitor use. We will discontinue the use of it on a subject if he/she is not able to tolerate it.

In order to lessen the risk of breach of confidentiality, subjects will be allowed to address their question and concerns in private with the research coordinator, study nurse and/or research physician. At any time during the study the patient is able to place privacy

restriction to their protected health information (i.e. telephone message, PHI release forms) which the study personnel document and respect. All data records will be stored on password protected computers and or in locked cabinets within the research department. These files will only be accessible by authorized study personnel

21.3 If applicable, indicate which procedures may have risks to the subjects that are currently unforeseeable.

Response: tDCS. There is no long term study on the safety of tDCS. As a result, the long term risk of this procedure is currently unforeseeable.

21.4 If applicable, indicate which research procedures may have risks to an embryo or fetus should the subject be or become pregnant.

Response: There is no known risk of using tDCS in pregnant subjects. However, since we do not have long term safety data on this issue, pregnant subjects will be excluded.

21.5 If applicable, describe risks to others who are not subjects.

Response: not applicable

22.0 Potential Benefits to Subjects

22.1 Describe the potential benefits that individual subjects may experience by taking part in the research. Include the probability, magnitude, and duration of the potential benefits. Indicate if there is no direct benefit.

*NOTE: Compensation **cannot** be stated as a benefit.*

Response: there is no direct benefit to participating in this research study.

23.0 Compensation for Research-Related Injury

- N/A:** The research procedures for this study do not present risk of research related injury (e.g. survey studies, records review studies). This section does not apply.

23.1 If the research procedures carry a risk of research related injury, describe the available compensation to subjects in the event that such injury should occur.

Response: Routinely, Buffalo General Hospital, Erie County Medical Center, and/or the University at Buffalo, State University of New York, its agents, or its employees do not compensate for or provide free medical care for human subjects/participants in the event that any injury results from participation in a human research project. In the unlikely event that they become ill or injured as a direct result of participating in this study, they may receive medical care, but it will not be free of charge even if the injury is a direct result of their participation.

23.2 *Provide a copy of contract language, if any, relevant to compensation for research related injury.*

*NOTE: If the contract is not yet approved at the time of this submission, submit the current version here. If the contract is later approved with **different language regarding research related injury**, you must modify your response here and submit an amendment to the IRB for review and approval.*

Response: N/A

24.0 Economic Burden to Subjects

24.1 *Describe any costs that subjects may be responsible for because of participation in the research.*

NOTE: Some examples include transportation or parking.

Response: transportation fee

N/A: This study is not enrolling subjects, or is limited to records review procedures only. This section does not apply.

25.0 Compensation for Participation

25.1 *Describe the amount and timing of any compensation to subjects, including monetary, course credit, or gift card compensation.*

Response: Each subject will be compensated 50 dollars for each visit they participate. They will also be compensated 10 dollars for parking. They will receive a check at the end of the study or their last visit.

N/A: This study is not enrolling subjects, or is limited to records review procedures only. This section does not apply.

N/A: There is no compensation for participation. This section does not apply.

26.0 Consent Process

26.1 *Indicate whether you will be obtaining consent.*

NOTE: This does not refer to consent documentation, but rather whether you will be obtaining permission from subjects to participate in a research study. Consent documentation is addressed in Section 27.0.

Yes *(If yes, Provide responses to each question in this Section)*

No *(If no, Skip to Section 27.0)*

26.2 *Describe where the consent process will take place. Include steps to maximize subjects' privacy.*

Response: All participants will come to the research department to be consented. Participants will be placed in a private room where they can review the consent. Participant questions and or concerns will be address with a member of the study team or research doctor if applicable.

26.3 Describe how you will ensure that subjects are provided with a sufficient period of time to consider taking part in the research study.

NOTE: It is always a requirement that a prospective subject is given sufficient time to have their questions answered and consider their participation. See “SOP: Informed Consent Process for Research (HRP-090)” Sections 5.5 and 5.6.

Response: A prospective subject will be given sufficient time to have their questions answered and consider their participation. And we call a potential subject before the screening visit, so they will have sufficient time to think about it before coming to our research unit.

26.4 Describe any process to ensure ongoing consent, defined as a subject’s willingness to continue participation for the duration of the research study.

Response: Subjects has the right to discontinue participation at any stage of the study

26.5 Indicate whether you will be following “SOP: Informed Consent Process for Research (HRP-090).” If not, or if there are any exceptions or additional details to what is covered in the SOP, describe:

1. *The role of the individuals listed in the application who are involved in the consent process*
2. *The time that will be devoted to the consent discussion*
3. *Steps that will be taken to minimize the possibility of coercion or undue influence*
4. *Steps that will be taken to ensure the subjects’ understanding*

Response:

We have reviewed and will be following “SOP: Informed Consent Process for Research (HRP-090).”

Non-English Speaking Subjects

N/A: This study will not enroll Non-English speaking subjects.
(*Skip to Section 26.8*)

26.6 Indicate which language(s) other than English are likely to be spoken/understood by your prospective study population or their legally authorized representatives.

NOTE: The response to this Section should correspond with your response to Section 6.4 of this protocol.

Response:

26.7 *If subjects who do not speak English will be enrolled, describe the process to ensure that the oral and written information provided to those subjects will be in that language. Indicate the language that will be used by those obtaining consent.*

NOTE: Guidance is provided on “SOP: Informed Consent Process for Research (HRP-090).”

Response:

Cognitively Impaired Adults

N/A: This study will not enroll cognitively impaired adults.
(Skip to Section 26.9)

26.8 *Describe the process to determine whether an individual is capable of consent.*

Response:

Adults Unable to Consent

N/A: This study will not enroll adults unable to consent.
(Skip to Section 26.13)

When a person is not capable of consent due to cognitive impairment, a legally authorized representative should be used to provide consent (Sections 26.9 and 26.10) and, where possible, assent of the individual should also be solicited (Sections 26.11 and 26.12).

26.9 *Describe how you will identify a Legally Authorized Representative (LAR). Indicate that you have reviewed the “SOP: Legally Authorized Representatives, Children, and Guardians (HRP-013)” for research in New York State.*

NOTE: Examples of acceptable response includes: verifying the electronic medical record to determine if an LAR is recorded.

Response:

We have reviewed and will be following “SOP: Legally Authorized Representatives, Children, and Guardians (HRP-013).”

26.10 ***For research conducted outside of New York State, provide information that describes which individuals are authorized under applicable law to consent on***

behalf of a prospective subject to their participation in the research. One method of obtaining this information is to have a legal counsel or authority review your protocol along with the definition of “legally authorized representative” in “SOP: Legally Authorized Representatives, Children, and Guardians (HRP-013).”

Response:

